1.0 Objectives

1.1 Study Objectives

The specific objective of this proposal is to utilize the practice of telemedicine via connected health devices to enable the guided performance of a remote pulmonary function test (rPFT) in the home. The rationale for this study is to determine whether telemonitoring of respiratory health can help exceed standards of ALS care.

Part 1: Demonstrate the reliability of remote pulmonary function testing, performed via telemedicine, for monitoring respiratory function in patients with amyotrophic lateral sclerosis (ALS)

Primary Hypothesis: There is no difference in the results of PFT and rPFT for respiratory assessment of FVC and MIP.

Secondary Hypothesis: The respiratory therapist, patient, and caregiver will express confidence in conducting the rPFT, as determined by surveys of procedure acceptance.

Part 2: Weekly remote pulmonary function testing (rPFT) and nurse respiratory health coaching (NRHC) in ALS telemedicine

This part randomizes subjects into two arms – both perform weekly rPFT testing and one receives monthly NRHC.

Aim 1: Clinically-meaningful benefit of weekly rPFT

Primary Hypothesis: Home respiratory assessment enables thresholds for non-invasive ventilation (NIV) recommendation to be met on average 30 days sooner when measured weekly compared to the standard 3-month interval.

Secondary Hypothesis: Determine the factors associated with adherence to weekly rPFT procedures.

Aim 2: The impact of NRHC on patient outcomes

Primary Hypothesis: Patient and caregiver teams in the NRHC arm report higher self-efficacy in the respiratory management of the disease at 6 months compared to those in the non-NRHC arm.

Secondary Hypotheses: Patients in the NRHC arm report higher self-efficacy at 12 months, experience less decline of respiratory-related quality of life and fewer respiratory complications compared to those in the non-NRHC arm.

1.2 Primary Study Endpoints

Part 1: The primary endpoint is completion of a standard PFT and an experimental rPFT during a single clinic appointment. At the endpoint, study outcomes will include:

- 1) The best forced vital capacity (FVC) and maximal inspiratory pressure (MIP) results from that visit's PFT
- 2) The best FVC and MIP results from that visit's rPFT
- 3) Survey responses from study participants.

Part 2: The primary endpoint for Aim 1 occurs at the clinic visit following initiation of NIV. At this time, participants will have had weekly measurements of FVC and MIP from self-administered rPFT procedures, as well as standard PFT assessments performed with the assistance of the respiratory therapist at approximately three-month intervals during standard in-person or telehealth clinic appointments. The primary endpoint for Aim 2 will be the change in self-efficacy scores from baseline. Changes will be compared across arms.

1.3 Secondary Study Endpoints

In Part 2: All participants will undergo a training period for rPFT procedures, which entails weekly rPFT coaching by a member of the research team for the first four weeks. To proceed with the remainder of the study, the participant team must demonstrate the ability to perform and transmit rPFT results to the research team during the 4th rPFT training session, and demonstrate FVC test results that are within 10% of the mean values achieved during the first three training sessions. Training sessions will occur at

weeks 8 and 12 to monitor aptitude. Changes in self-reported respiratory quality of life will be measured as part of procedures in Part 2. Participants completing the study may be offered the opportunity to participate in a focus group on their experience in the study, which will be conducted via Penn State Health Zoom videoconferencing and have audio recorded.

2.0 Background

2.1 Scientific Background and Gaps

Non-invasive ventilation (NIV) lengthens survival and improves QoL for patients with ALS.

According to the Quality Measurement Set put forth by the American Academy of Neurology (AAN), two parameters of high importance in ALS care are monitoring of respiratory function and management with NIV [Miller2013]. The practice parameter of the AAN regarding ALS care states that NIV is effective in prolonging survival and slowing the rate of respiratory decline [Miller2009]. NIV has been documented to have a positive effect on QoL in the areas of sleep quality, daytime sleepiness, physical fatigue, and depression [Butz2003]. NIV is recommended when a patient presents with either an FVC \leq 50% predicted or a MIP > -60 cm H₂O [Miller2009]. It is recommended that PFTs be done at least once every three months, and that doctors discuss options for NIV support regularly.

The multidisciplinary clinical model may not provide optimal management for patients with rapidly progressing respiratory symptoms.

Although disease course varies substantially, some patients experience rapid respiratory decline. In prospective study of 38 newly diagnosed patients, half presented with chronic hypoventilation after one year, necessitating the introduction of NIV [LoCoco2006]. The authors suggest that efforts should be made to evaluate pulmonary function in these patients at least once every month. Furthermore, it has been shown that early initiation of NIV at an FVC threshold of 65% predicted was associated with a significant increase in the median time from ALS diagnosis to death [Lechtzin2007]. The current practice of quarterly respiratory assessment may leave some individuals in danger of developing to untreated respiratory insufficiency or beginning treatment later than would be optimal or other more scientific wording.

Telemedicine has impacted other areas of neurology, but is understudied for efficacy in ALS.

The practice of telemedicine involves the delivery of medical care via long-distance and electronic communication between a health care professional and a patient or another health care professional. This type of intervention can expand medical coverage into underserved regions, while maintaining the high quality of care. Success with telemedicine in other areas of neurology, such as in the treatment of Parkinson's disease [Samii2006], epilepsy [Ahmed2008], and stroke [Demaerschalk2009], provide a framework for achieving positive outcomes.

It is largely unknown whether remotely-provided multidisciplinary care results in outcomes for ALS patients and their caregivers that are comparable to those achieved with traditional care. A review by Hobson et al. identified 32 publications addressing telemedicine in ALS [Hobson2016], which concluded that patients are comfortable using the videoconferencing interface to discuss most concerns, they appreciated the reduced travel time and costs, and the use of telemedicine extended the period for which they received multidisciplinary care. Some programs offered live interaction with providers as a way to delivered care to individuals in rural areas with no alternative treatment options [ALS-Maine2010, Bedlack2014]. Other models utilized a traveling nurse to perform the assessment in the patient's home, which is stored and forwarded to the appropriate providers at the multidisciplinary clinic [Pulley2015, McClellan2013]. Others have taken on a more passive role, with monitoring of oximetry and non-invasive ventilation (NIV) data by a nurse led to fewer hospital visits, and higher treatment adherence [Pinto2010, Vitacca2010, Ashcroft2016].

Despite these results, Hobson concludes “*There is limited evidence to recommend the use of telemedicine or telehealth in the case of patients with ALS. Using telehealth as an alternative to clinic visits appears technically feasible but further research needs to establish its safety and effectiveness*” [Hobson2016]. To address gaps in telemedicine care, randomized controlled clinical trials must be used to identify methods that can meet or surpass the standards of in-person assessment.

2.2 Previous Data

Preliminary work by our group as part of a pilot study assessing the benefits of ALS telemedicine has shown that the practice of live telemedicine is viewed favorably by ALS patients, caregivers, and multidisciplinary ALS team members, although less so by the latter group (Figure 1, [Morris2016, Geronimo2017]). Overall, the three rater groups were concerned that the lack of physical contact lessened the ability for providers to deliver equal care. This led us to identify and act upon one area of care that could be improved in telemedicine – assessment of breathing function.

[figure not shown]

Figure 1: Patient (P), caregiver (C), and health care provider (H) ratings of the ALS telemedicine pilot in four domains [Geronimo2017]. Circles containing an X mark the medians, thick lines span the first to third quartile of data, with thin lines extending up to two times this range. Outliers are those small circles outside this range

From January to September 2018, the procedures for part 1 were completed in forty patients. The main result was that the simulated remote assessment produced similar values of FVC and MIP compared to standard assessments (Figure 2). In this sample, the specificity and sensitivity of FVC measurements were 100%, for MIP assessments was 89% and 82%, respectively [Geronimo2019]. The results of part 1 indicate that rPFTs are accurate and acceptable measures of respiratory health.

[figure not shown]

Figure 2: FVC (Left) and MIP (Right) data from 40 subjects of the rPFT pilot study, comparing standard PFT measures to therapist-guided remote assessments. Four shaded quadrants are created by segmenting standard and remote tests by predefined clinical thresholds.

2.3 Study Rationale

The rationale for this study is to determine whether telemonitoring of respiratory health can help exceed standards of ALS care.

3.0 Inclusion and Exclusion Criteria

3.1 Inclusion Criteria

Part 1

Patients:

- 1) Possess a diagnosis of definite, probable, probable laboratory-supported, or possible ALS by revised El Escorial research criteria [Brooks2000], or a diagnosis of primary lateral sclerosis (PLS, upper motor neuron involvement only) or progressive muscular atrophy (PMA, lower motor neuron involvement only).
- 2) Be 18 years of age or older.
- 3) Have a caregiver available to participate in the study

Caregivers:

- 1) Be 18 years of age or older, of either gender.
- 2) Be able and willing to provide informed consent.

Controls:

- 1) Be 18 years of age or older, of either gender.
- 2) Be able and willing to provide informed consent.

Respiratory Therapist

- 1) Be a member of the Hershey Medical Center ALS multidisciplinary care team.
- 2) Be able and willing to provide verbal informed consent after receiving a summary explanation of research (SER).

Part 2:

Patients:

- 1) Possess a diagnosis of definite, probable, probable laboratory-supported, or possible ALS by revised El Escorial research criteria.
- 2) Be 18 years of age or older.
- 3) Have a caregiver available to assist with home PFTs or, in the opinion of the investigator, can perform home PFTs unassisted.
- 4) Symptom onset within the last three years.
- 5) Have a computer and home internet service sufficient for engaging in telemedicine sessions.
- 6) Have a second device capable of downloading the spirometer application from an app store (Android- or iOS-based smartphone or tablet).

Caregivers (not necessary to be enrolled if patient can perform home PFTs unassisted):

- 1) Be 18 years of age or older, of either gender.
- 2) Be able and willing to provide informed consent.

3.2 Exclusion Criteria

Part 1

Patients:

- 1) Cognitive impairment, as judged by the ALS clinic neurologist, that prevents participation in the study.
- 2) Unable to perform pulmonary function testing with mouthpiece or with mask, as determined by one of the study investigators.

Caregivers: None

Controls: None

Respiratory Therapists: None

Part 2 imposes additional exclusion criteria for patients only.

Patients:

- 3) Use of NIV or diaphragm pacer at time of obtaining informed consent.
- 4) FVC \leq 50% predicted

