7.0 Study Design and Procedures

7.1 Study Design

Part 1: This is a self-controlled study where each participant will be administered a standard of care PFT for measurement of FVC and MIP, as well as an rPFT, separated by at least an hour, for measurement of

experimental FVC and MIP. The rPFT is guided by a respiratory therapist in another room, utilizing the telemedicine interface of the Hersey ALS clinic and devices for measuring FVC and MIP (**Error! Reference source not found.**).

[figure not shown]

Figure 3: Tools for remote pulmonary testing. Left: Air Smart Spirometer and turbine. Right: respiratory pressure meter and mouthpiece.

Part 2: This is a two-arm, randomized study to determine 1) whether weekly monitoring of respiratory function can lead to timelier initiation of NIV and 2) whether structured nurse coaching leads to improved self-efficacy for managing disease and better maintenance of respiratory health. For enrollees in both arms, standard FVC and MIP measurements obtained approximately every three months by the respiratory therapist during ALS Clinic are supplemented with self-administered rPFTs performed weekly. To train the participant in the performance of rPFTs, a member of the research team will be present either in person or virtually to guide the patient and caregiver in the appropriate use of the equipment during the first four weeks of the study. Enrollees in the NRHC arm will additionally receive monthly coaching with the study nurse via telehealth. Approximately 5% of NRHC sessions will include audio recordings that will be evaluated by a second clinician nurse for quality and consistency.

rPFT protocol

Two devices are used to measure respiratory function:

- 1) Air Smart Spirometer, NuvoAir AB

The following information is paraphrased from the user manual, which is included in the “devices” page of the protocol.

The Air Smart Spirometer measures the forced vital capacity (FVC) in a forced expiratory maneuver. The Air Smart Spirometer is intended to be used by:

- Healthcare professionals trained to perform spirometry tests on patients.
- Adults trained by healthcare professionals or through self-learning who understand how to perform a high quality spirometry test.

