During each guided rPFT administration, a member of the research team and/or respiratory therapist will guide the patient and caregiver through three valid maneuvers of the FVC and MIP tests. The participants prepare the spirometer by connecting it to the tablet and opening the associated application. The patient is told to sit as upright as possible for the measurement of FVC. They will be told that to do this they will 1) inhale maximally, 2) exhale as hard and fast as possible, and 3) continue to exhale until indicated by the therapist. The researcher will also demonstrate this procedure to the patient. The caregiver applies nose clips to block airflow through the nose, holds the turbine of the spirometer to the patient's mouth and performs three repetitions of this sequence, with periods of relaxation between testings. Testing is repeated until three valid maneuvers are achieved. The application on the tablet computes the FVC and percentage predicted value, the best of which is retained.

To perform the MIP test, the participant inserts the mouthpiece into the pressure meter. The patient is told they will be asked to draw breath in as quickly and powerfully as possible, for at least one second. The researcher tells the caregiver to place a finger over the valve outlet so that no air flows through the mouthpiece during inhalation. Nose clips will be used. The patient performs three repetitions of this task. The maximal negative pressure from a valid run is recorded.

Each piece of reusable equipment will be labeled with an identification number. A log of all loaned materials will be maintained by the researchers. This log, included in the supporting documents, will be maintained on REDCap. Before delivery of the system to the study participant, each piece of equipment will be inspected and tested. This study will not collect prior medical therapy relevant to the use of the device. There are no restrictions on medicines or therapies used by the participants in this study.

Randomization (Part 2 only)

An unblinded blocked minimization method will randomize participants based on demonstrated factors affecting prognosis [Chio2009]. These include: time since diagnosis, age at consent, most recent FVC, and FVC slope from up to the previous year, if available.

NRHC protocol (Part 2 only)

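### Aim 1 sets no at-risk rule for MIP: untreated patients already past the MIP limit at their last standard PFT can enrol, and the Figure 4 outcome then credits rPFT with days that are not lead time

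*Combined protocol and SAP*

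**What the plan says.** **NIV criterion.** Section 2.1 gives the indication as an FVC at or below "50% predicted or a MIP > -60 cm" H₂O. Section 7.2.2 uses the same either-or rule for sending a test report to the clinical team.

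**Entry.** For Part 2 patients, section 3.2 adds two exclusions: "Use of NIV or diaphragm pacer at time of obtaining informed consent" and "FVC \leq 50% predicted". No entry criterion concerns MIP. Minimization uses "time since diagnosis, age at consent, most recent FVC, and FVC slope from up to the previous year, if available", again without MIP. Section 7.2.2 collects PFT history, but no Aim 1 rule uses it. Section 3.3.1 allows removal of a participant who shows an exclusion criterion, but MIP is not one.

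**Aim 1 outcome.** Four places describe it differently:
- Section 1.1 hypothesises that home testing allows the thresholds for an NIV "recommendation to be met on average 30 days sooner when measured weekly compared to the standard 3-month interval".
- Section 1.2 states: "The primary endpoint for Aim 1 occurs at the clinic visit following initiation of NIV".
- The Figure 4 legend (section 7.2.2) defines Δ as the time from when NIV need is first detected to the following routine visit.
- Section 8.3 compares the date of NIV initiation according to rPFTs with the date according to clinic PFTs, and names no analysis set.

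**Tests available.** Section 7.1 has "standard FVC and MIP measurements obtained approximately every three months by the respiratory therapist during ALS Clinic", so the clinic already measures MIP. Section 1.2 says that by the endpoint "participants will have had weekly measurements of FVC and MIP from self-administered rPFT procedures". The sessions of the first four weeks are guided, and the plan does not say which rPFT is the first that counts.

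**The concern.** Lead time over quarterly testing exists only if the last quarterly test was negative. If that test had already met the MIP criterion, the standard schedule had found the need and weekly testing could not find it sooner. The Figure 4 Δ still gives such a patient a positive number of days, because it runs forward to the next visit. Dating the first detection to the earlier clinic PFT does not help, since Δ would still run to the next visit.

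The error has one direction, toward rPFT, and it enters the quantity on which the 30-day claim rests. The Figure 4 legend refers to a crossing of the threshold, which suggests that new crossings are meant, but it is a legend and sets no analysis rule.

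The issue is confined to patients whose last standard PFT was already MIP-positive. Someone who crossed after that PFT but before the first rPFT, which is plausible with remote consent, has a real lead and should count.

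**Working it through.** **The plan's own figures.** Section 8.1 plans 40 completers and section 8.2 expects 75% to reach the NIV criteria: 40 × 0.75 = 30, or 15 per arm, as stated. With no alpha stated, a one-sided 5% t-test at effect size 0.95 has 81.4% power with 15 per arm, consistent with the stated 80%; a two-sided test has 70.9%. The decline studies and the simulation behind these figures use FVC only, so MIP status at entry plays no part in them. The 47 rPFTs in section 7.3 equal 52 weeks minus 5 clinic PFTs. This suggests that the guided weeks are in that count; without them it would be 43.

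**Assumptions for the illustration.** Figure 4 Δ; clinic visits at weeks 0 and 13; error-free rPFTs in weeks 1 to 12; new crossings equally likely in each week.

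**New crossings.** Δ takes the values 84, 77, …, 7, 0.
- Mean = 7 × (0 + 1 + … + 12)/13 = 42 days.
- SD = 7 × √((169 − 1)/12) = 26.2 days.
- If guided weeks 1 to 4 of the first interval do not count, crossings in weeks 1 to 5 each score 56, and the rest run from 49 down to 0. The first-interval mean is (5 × 56 + 196)/13 = 36.6. Over four intervals: (36.6 + 3 × 42)/4 = 40.7.

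**Already MIP-positive at week 0.** The credited days are:
- counting from week 5: (13 − 5) × 7 = 56
- counting from week 1: (13 − 1) × 7 = 84
- remote starts spread evenly over weeks 1 to 12: mean of 7, 14, …, 84 = 45.5

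Week 5 is the better-supported start, because sections 1.2 and 7.1 speak of self-administered tests.

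**Effect on the mean.** For an already-positive share p, the credited mean is (1 − p) × 42 + p × c, where c is the credit. The shift per 10 points is 0.1 × (c − 42) = 1.4, 4.2 or 0.35 days.

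| Assumed share p | c = 56 (week 5) | c = 84 (week 1) | c = 45.5 (remote) |
|---|---|---|---|
| 10% | 43.4 | 46.2 | 42.4 |
| 20% | 44.8 | 50.4 | 42.7 |
| 30% | 46.2 | 54.6 | 43.1 |
| 40% | 47.6 | 58.8 | 43.4 |

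With the 40.7 base and c = 56, the means are 42.2, 43.7, 45.3 and 46.8.

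**When it would decide the claim.** The pooled mean reaches 30 days when the true mean for new crossings is (30 − p × c)/(1 − p). At p = 20% this is (30 − 11.2)/0.8 = 23.5 days for c = 56, and (30 − 16.8)/0.8 = 16.5 days for c = 84. True leads between those values and 30 would be reported as meeting the target.

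**Under the section 8.3 wording.** If the positive week-0 PFT sets the clinic date, an rPFT date in week 1 or week 5 gives a lead of −7 or −35 days, or zero if negative values are not allowed. The same patient thus scores between +84 and −35 days depending on which section is followed.

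**The case against.** The strongest reply is that the credited days exist only under the Figure 4 legend. Section 8.3 is the statistical section, and under its wording an already-positive patient may bring rPFT no gain at all. That stands: the conflict between the outcome wordings comes first, and settling it could remove much of the problem. It does not remove the gap, because Figure 4 is the only place that writes the outcome as a measurable interval.

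The effect may also be small. MIP past the limit is itself an NIV indication and NIV users are excluded, so only untreated patients remain, possibly few. Some might trigger a report during guided training, start NIV, stop rPFT and contribute no counted Δ. Both points limit the size but leave the direction unchanged.

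The error-free assumption is generous. Section 2.2 reports MIP specificity of 89%. If weekly tests were independent, 12 of them would give at least one false trigger in 1 − 0.89¹² = 75% of truly negative patients. That is a separate source of credited days, which an at-risk rule would not touch.

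Two stronger readings are tempting:
- A reader might infer that the gap overturns the 30-day claim. If already-positive patients count at zero lead, the mean is (1 − p) × 42, which falls below 30 once p exceeds 1 − 30/42 = 28.6%. That needs a target covering everyone who meets the criterion. Sections 1.1 and 8.2 and the Figure 4 legend point instead to patients who decline to the threshold during the study.
- A reader might infer a large share from Part 1. If all 40 patients had MIP results, the 82% sensitivity and 89% specificity fit only 18/22 and 16/18, so 22 of 40 (55%) were positive on the standard test. Part 1 did not exclude NIV users or low FVC, so this cannot be carried over to Part 2.

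**Conclusion.** The gap is real. NIV need has two alternative triggers, entry screens on one of them, and no Aim 1 rule requires a negative standard PFT first. Under the Figure 4 Δ, the days credited to an already MIP-positive patient are not lead time and always favour rPFT.

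The size is unknown, because the documents give no Part 2 share; the 10% to 40% used above are assumptions. In the illustration the inflation is modest on the better-supported start, and larger only if the guided tests count from week 1. New crossings already average more than 30 days there, so the bias alone does not change that conclusion. It would matter if their true lead were below 30 days, as the plan cannot rule out. The documents do not support saying that the Aim 1 result is invalid or that the 30-day claim would reverse. The point should be settled before analysis, together with the outcome definition.

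**What to change.** In section 8.3:
1. Fix one Aim 1 outcome, and bring sections 1.1, 1.2, 7.2.2 (with Figure 4) and 8.3 into line with it.
2. State which rPFT is the first that counts.
3. Define the primary Aim 1 set as participants whose last standard PFT before that rPFT met neither NIV criterion, using the MIP that the clinic already measures. Record that value explicitly, since PFT history does not name it.
4. Report how many participants were already MIP-positive. Run a sensitivity analysis that includes them, once as credited and once at zero lead, together with participants who have no prior standard MIP.
5. Keep everyone in Aim 2.

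The study team should also reconcile the NIV criterion in sections 2.1 and 7.2.2 with the exclusions in section 3.2. No clinical threshold is proposed here.

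**Cost.** A few sentences and one data check, with no change to care. The real downside is fewer evaluable Aim 1 patients. At a 20% share, 30 become 24, and the 95% half-width of mean Δ, t × 26.2/√n, widens from 9.8 to 11.1 days. Patients from outside the clinic (section 4.4) who lack a prior MIP would also leave the primary set; the documents do not allow that loss to be estimated.
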